4.10.2. Clinical Laboratory Evaluations

Hematology laboratory assessments will include white blood cell count with differential, hemoglobin, hematocrit, mean corpuscular volume, mean corpuscular hemoglobin, mean corpuscular hemoglobin concentration, total red cell count with morphology, and platelet count. These parameters will be measured at all study visits.

Biochemistry laboratory assessments will include sodium, potassium, chloride, bicarbonate, blood urea nitrogen, creatinine, magnesium, calcium, phosphorus, uric acid, glucose, total protein, albumin, globulin, albumin:globulin ratio, bilirubin (total, direct and indirect), creatine kinase (CK), lactate dehydrogenase (LDH), alanine aminotransferase (ALT), aspartate aminotransferase (AST), gamma glutamyl transferase (GGT), alkaline phosphatase, total cholesterol, high-density lipoprotein (HDL), low-density lipoprotein (LDL), triglycerides, and cystatin C. These parameters will be measured at all study visits. Ideally, subjects should have fasted for at least 8 hours prior to blood collection.

Urinalysis assessments will include pH, specific gravity, glucose, ketones, blood, protein, creatinine, urobilinogen, bilirubin, nitrite, and leukocyte esterase. These parameters will be measured at all study visits.

Hematology, serum biochemistry, and urinalysis data and their changes from baseline (only for continuous laboratory parameters) will be summarized by visit. Maximal and minimal change from baseline in each parameter will also be summarized.

Shift tables for hematology, serum biochemistry, and urinalysis will also be presented showing change in CTCAE severity grade from baseline to each visit. For parameters for which a CTCAE scale does not exist, shift tables will be presented showing change in results from baseline (normal, low, and high [or abnormal]) to each visit (normal, low, and high [or abnormal]).

Frequency tables will be presented for safety monitoring parameters to show the number and percentages of subjects by severity grade categories defined in [Table 2](#). If a CTCAE grade does not exist, abnormal results will be summarized by protocol-defined thresholds as noted in [Table 2](#). Subjects will be characterized only once for a given assay, based on their worst severity grade observed during the time period of interest.

By-subject listings will be provided for viral screen (hepatitis B surface antigen, hepatitis C antibody, human immunodeficiency virus (HIV)), Serum beta chorionic gonadotropin (β -HCG), and CFTR gene sequencing in addition to the above mentioned clinical laboratory tests.

As necessary, laboratory abnormalities will be described by duration of study drug exposure, by dose, by age group, by sex, by race, by weight, and for special populations (eg, antibiotic use).

Table 2. Safety Monitoring Parameters and Actions To Be Taken

Organ System and Laboratory Parameter	Stop Study Drug Immediately, Confirm^a Abnormal Value, and Then Start Work-Up	Stop Study Drug After Confirming^a Abnormal Value, and Then Start Work-Up	Continue Study Drug, Confirm^a Abnormal Value, and then Start Work-Up
Hepatic			
Serum total bilirubin ^b	≥Grade 3 (≥3.0 x ULN)	Grade 2 (1.5 – 3.0 x ULN)	---
Serum ALT	≥Grade 3 (≥5.0 x ULN)	Grade 2 (>2.5 – 5.0 x ULN)	---
Serum AST	≥Grade 3 (≥5.0 x ULN)	Grade 2 (>2.5 – 5.0 x ULN)	---
Serum GGT	≥Grade 3 (≥5.0 x ULN)	Grade 2 (>2.5 – 5.0 x ULN)	---
Renal			
Serum cystatin C	>2.00 mg/L	>1.33 – 2.00 mg/L	---
Serum creatinine	≥ Grade 2 (≥1.5 x ULN for age)	Grade 1 (>ULN – 1.5 x ULN for age)	---
Serum BUN	≥3.0 x ULN	≥1.5 – 3.0 x ULN	---
Urine protein: urine creatinine (spot)	---	>0.40 mg:mg	---
Urine blood (by dipstick)	4+ (in absence of menstruation)	3+ (in absence of menstruation)	2+ (in absence of menstruation)

^a Laboratory abnormalities may be confirmed immediately or based on investigator judgment.

^b Patients with a diagnosis of Gilbert's syndrome need not confirm the laboratory parameter and/or stop study drug unless the total bilirubin value exceeds 3.0 x ULN

Abbreviations: ALT = alanine aminotransferase, AST = aspartate aminotransferase, BUN = blood urea nitrogen, Ca²⁺ = calcium, GGT = gamma glutamyl transferase, HCO₃⁻ = bicarbonate, K⁺ = potassium, Mg²⁺ = magnesium, Na⁺ = sodium, ULN = upper limit of normal

I

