In the Phase 3 clinical trial (Study 009), serious adverse events related to renal dysfunction, which occurred only in the ataluren arm, included 3 patients with acute renal failure, 3 patients with renal failure, and 1 patient with hypercreatininemia. These events were characterized by elevated creatinine (Grade 1 to Grade 4), which resolved over days to weeks. Only 1 patient experienced symptoms of renal dysfunction (transient oliguria). All 7 events were associated with concomitant systemic treatment with potentially nephrotoxic antibiotics (eg, aminoglycosides, vancomycin) that were generally administered as treatment for pulmonary exacerbations. No patient required dialysis. One patient was unblinded and 1 patient chose not to continue study drug treatment; the remaining 5 of 7 patients restarted study medication and continued study participation without recurrent creatinine elevations. This issue was recognized during the conduct of the study and changes were made in the protocol (eg, prohibition of concomitant use of potentially nephrotoxic agents), which successfully addressed the issue. Non-serious creatinine elevations occurred predominantly in the ataluren arm and were transient, generally mild, and resolved with or without interruption of study medication. The incidence of treatment emergent nephrolithiasis was similar in the ataluren and placebo groups.

The renal monitoring program included in this protocol considers nonclinical and clinical findings with ataluren, and past experience with known nephrotoxins. Concomitant use of potentially nephrotoxic antibiotics with ataluren is prohibited. A focus is placed on well-established clinical indicators of renal dysfunction for making diagnostic decisions and prompting treatment interruptions/modifications in individual patients. The rationale for each of the decision-making parameters is discussed below.

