#### 14.2.3.1.2. Renal Monitoring Plan

- **Serum Creatinine:** Given the widespread clinical familiarity with serum creatinine as a marker of renal dysfunction and as a monitoring tool for nephrotoxins in clinical practice [Gilead 2002, Gilead 2006, Novartis 2005], characterization of serum creatinine provides an appropriate frame of reference relative to other experiences.
- **Serum Cystatin C:** An alternative to assessing GFR based on serum creatinine, serum cystatin C offers advantages in the assessment of renal function in the context of this protocol. Cystatin C is a low-molecular-weight (~13 kDa) proteinase inhibitor derived from all cells that is filtered by the glomerulus and degraded in the renal tubules [Herget-Rosenthal 2007]. The serum cystatin C concentration is almost solely dependent upon GFR and appears relatively unaffected by muscle mass or other conditions. An additional advantage is that circulating cystatin C changes more rapidly in response to multiple types of renal injury than creatinine [Herget-Rosenthal 2007]. Methods for measuring cystatin C are standardized and the correlations between serum cystatin C and GFR have been derived and confirmed in large studies involving healthy children and adults and those with renal dysfunction [Dharnidharka 2002, Grubb 2005, Zappitelli 2007]. Based on these considerations, values of serum cystatin above 1.33 mg/L should prompt diagnostic evaluation and interruption/modification of study drug if required per protocol.

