Listings of death, serious AEs, AEs leading to discontinuation from treatment, and adrenal, hepatic and renal AEs leading to special diagnostic evaluations will be provided. Renal AEs for subjects not using nephrotoxic concomitant medications, subjects using nephrotoxic concomitant medications, and subjects with postbaseline creatinine $> 1.5 \times \text{ULN}$ will also be listed, separately.

The drug exposure adjusted TEAE incidence rate will be summarized by SOC and PT, where the incidence rate of the TEAE per 100 patient-year = (number of events/number of patient-years) $\times 100$. The number of patient-years is defined as the sum of the number of days on study drug of all patients divided by 365.25.

In addition, the number of subjects with clinical laboratory abnormalities, abnormal vital signs, and abnormal electrocardiogram reported as TEAE will be summarized.

Non-serious TEAE will be displayed by SOC and PT. The common non-serious TEAE (subject frequency of $\geq 5\%$) will also be displayed by SOC and PT.

Numbers of occurrence of serious TEAE and the numbers of occurrence of non-serious TEAE will be summarized by SOC and PT, separately.

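### Creatinine change is pooled over minors and adults and never counted against the subject's own baseline, so the mean mixes growth with any drug effect and a doubling from half the ULN or less is ungraded

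*SAP*

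**What the plan says.** Laboratory abnormalities are part of the primary endpoint (SAP 2.3.1). SAP 4.10.2 plans these outputs for them in the As-Treated population:

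- By-visit summaries: "Hematology, serum biochemistry, and urinalysis data and their changes from baseline (only for continuous laboratory parameters) will be summarized by visit".
- Extremes: "Maximal and minimal change from baseline in each parameter will also be summarized".
- Shift tables "presented showing change in CTCAE severity grade from baseline to each visit".
- Frequency tables that "show the number and percentages of subjects by severity grade categories defined in" SAP Table 2. Creatinine is Grade 1 there from above the ULN for age, and Grade 2 or higher from "1.5 x ULN for age".
- Breakdown of laboratory abnormalities by age group, sex, weight and other factors, but only where judged necessary. The change tables are not mentioned in that sentence.

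SAP 4.10.1 adds three renal adverse event listings. One of them is for "subjects with postbaseline creatinine" above 1.5 x ULN.

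Cystatin C is measured at every visit and has its own limits in Table 2. Protocol 14.2.3.1.2 explains its use: "serum cystatin C concentration is almost solely dependent upon GFR and appears relatively unaffected by muscle mass or other conditions".

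**The concern.** Renal toxicity is the main identified risk. In Study 009 all seven renal serious adverse events were in the ataluren arm, with creatinine at Grades 1 to 4. Of the remainder the protocol says: "Non-serious creatinine elevations occurred predominantly in the ataluren arm and were transient, generally mild" (Protocol 14.2.3.1.1).

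Two features of the plan limit what the creatinine tables can show.

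1. Participants are at least 9 years old (Protocol 14.1.2) and treatment is planned for 192 weeks. Creatinine tends to rise as a child grows, even with stable kidney function. Table 2 concedes this by using an age-specific ULN. In Study 009 the placebo arm allowed growth to be subtracted, and Protocol 14.1.4 relies on that Week 48 comparison to conclude that there was no cumulative renal effect. This study has no such arm, and its change tables are neither split nor standardised by age.
2. Every graded creatinine count is a multiple of the ULN. A large rise within one subject from a low starting value can end below the ULN, and then no table counts it as an event.

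The SAP does adjust for age elsewhere: blood pressure in minors by height and age nomogram (4.11.1), and weight and height by growth-chart percentile (4.12.2).

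**Working it through.** The documents give no calculation on this point, so there is no figure to reproduce.

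**Grading arithmetic (from SAP Table 2 alone).** Let the baseline be f x ULN for age and the rise k-fold. The value is graded only if k x f > 1, and is Grade 2 or higher if k x f >= 1.5.

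- Doubling (k = 2): ungraded for f <= 1/2 = 0.50; Grade 1 for f above 0.50 and below 0.75; Grade 2 or higher from f = 0.75.
- 1.5-fold rise (k = 1.5): ungraded for f <= 1/1.5 = 0.67.
- Example: 0.40 x ULN doubles to 0.80 x ULN, no grade. 0.30 x ULN triples to 0.90 x ULN, no grade.

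Inclusion criterion 5 requires screening values within the central laboratory range, which puts the screening value at or below the ULN. The lower limit of that range and the distribution of baselines are not given, so the number of subjects with f <= 0.50 or f <= 0.67 is unknown.

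**Growth drift in the pooled mean (illustration only).** Drift = share of minors x yearly rise in minors x years. The planned duration is 192 x 7 / 365.25 = 3.68 years and planned enrolment is about 70. All other inputs are assumptions: minors 20% to 60%; rise 0.02 to 0.05 mg/dL a year in minors and none in adults; SD of change 0.10 or 0.15 mg/dL; all 70 observed at Week 192. The SD used for the interval adds the spread between minors and adults.

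| Minors | Rise per year (mg/dL) | Mean change, Week 192 (mg/dL) | 95% CI, SD 0.10 | 95% CI, SD 0.15 |
|---|---|---|---|---|
| 20% | 0.02 | 0.2 x 0.02 x 3.68 = 0.015 | -0.010 to 0.039 | -0.021 to 0.051 |
| 40% | 0.03 | 0.4 x 0.03 x 3.68 = 0.044 | 0.018 to 0.071 | 0.007 to 0.082 |
| 60% | 0.05 | 0.6 x 0.05 x 3.68 = 0.110 | 0.079 to 0.142 | 0.069 to 0.151 |

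With no drug effect at all, the interval can include or exclude zero, depending on inputs that the documents do not supply. SAP 2.1 records early termination. Shorter follow-up reduces the drift in proportion (at half the duration the middle row becomes 0.022 mg/dL), and fewer subjects at late visits widen the intervals.

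**Share of minors.** Protocol 14.1.2 says that 65 patients (86.7%) under 18 completed Study 009 and are eligible. This implies 65/0.867 = 75 minors in that study. How many enter this one, and how many are still under 18, is not stated.

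**The case against.** The case against is substantial, and most of it stands as a limit on the point.

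- **Growth in the graded counts.** A reader might infer that growth will be graded as renal toxicity. Table 2 uses an age-specific ULN, so this is largely dealt with. The problem is confined to the change tables.
- **A doubling is hidden.** The documents do not support this. It enters the by-visit and maximal-change summaries and the by-subject listings. If it needs intervention or further investigation it is an adverse event (Protocol 9.1.1), and laboratory abnormalities reported as treatment-emergent events are tabulated (SAP 4.10.1). SAP 5.4 also defines relative change, although 4.10.2 does not ask for it. What stands is that no table counts such subjects.
- **A creatinine trend cannot be separated from growth.** This is too strong. Cystatin C is summarised in the same section, and the protocol describes it as little affected by muscle mass. But the two markers are not set side by side by age, and the age breakdown is optional and limited to abnormalities.
- **The 1.5 x ULN limit on the renal listing misses mild rises.** It does not. The other two listings, for users and non-users of nephrotoxic medication, together cover every subject. The third is an additional cut at the Grade 2 boundary. Grade 1 values are counted in the Table 2 frequency tables, so this listing needs no change.
- **Comparability.** CTCAE version 3.0 was kept so that results can be compared with earlier ataluren trials (Protocol 14.1.3.1), and the SAP treats all analyses as descriptive (4.2). Both are fair, but added tables leave the grading intact, and a descriptive mean with its confidence interval will still be read.

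**Conclusion.** The point holds in a limited form. The creatinine change tables pool minors and adults without a control arm, age split or age standardisation, so the mean change by visit combines growth with any drug effect. No output counts subjects by rise over their own baseline. A doubling from at or below 0.50 x ULN for age, or a 1.5-fold rise from at or below 0.67 x ULN, is therefore ungraded. Those thresholds follow directly from Table 2.

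The practical size cannot be established. The growth drift, the current share of minors and the number of low baselines are not in the documents, and the 0.015 to 0.110 mg/dL range rests on assumed inputs and full 192-week follow-up. A reader might take the share of minors in Study 009 as a ceiling for this study. It is not one: 65 completers who were minors then are eligible, against about 70 planned places, while an unknown number have since turned 18.

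Renal safety is not left unassessed. This is a worthwhile, inexpensive improvement to the primary safety analysis.

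**What to change.** Amend SAP 4.10.2, which SAP Section 1 allows before database lock:

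1. Present the creatinine change tables by age group (<18 and >=18 years, the grouping already in SAP 4.6), or as a multiple of the age-specific ULN at each visit.
2. Show the cystatin C change tables beside them with the same split.
3. Add the number and percentage of subjects with any post-baseline creatinine >=1.5 and >=2.0 times own baseline, by age group.
4. State that in minors these counts are to be read with cystatin C, because growth also raises creatinine.

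This is analysis only, on data already collected. It alters no grading rule and no subject's management. The cost is a few more tables, with wider intervals in the smaller age groups.

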#### **11.4.5.2. Laboratory Data**

Hematological, serum biochemistry, adrenal assessments, and urine data and their changes (only for continuous laboratory parameters) from baseline will be summarized by visit.

Hematological, serum biochemistry, adrenal assessments, and urine data will be graded according to CTCAE severity grade when applicable. For parameters for which a CTCAE scale does not exist, the frequency of subjects with values below, within, and above the normal ranges will be summarized. Summary tables will be presented for each relevant assay to show the number of subjects by severity grade with corresponding percentages. Subjects will be characterized only once for a given assay, based on their worst severity grade observed during the time period of interest.

Shift tables for hematology, serum biochemistry, adrenal assessments, and urine data will also be presented showing change in CTCAE severity grade from baseline to each visit. For parameters for which a CTCAE scale does not exist, shift tables will be presented showing change in results from baseline (normal, low and high [or abnormal]) to each visit (normal, low and high [or abnormal]).

Separate listings and tables will be created for assessment of adrenal, hepatic, and renal parameters based on the conditions listed in [Section 6.3.1](#).

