markers (protein and blood), and serum electrolytes (Na+, K+, HCO3, Mg2+, Ca2+, and phosphate).

During the Phase 2b double-blind study of ataluren in nmDMD (PTC124-GD-007-DMD), mean total cholesterol and triglycerides were in the upper range of normal at baseline and increased on study, reaching borderline high or high values. Baseline mean cholesterol and triglycerides values were higher in patients receiving systemic corticosteroid therapy. During the treatment period, increases in mean cholesterol levels were observed in patients receiving systemic corticosteroid therapy, more prominently in ataluren-treated patients than in the placebo arm. In patients not receiving systemic corticosteroid therapy, mean cholesterol levels increased similarly across all 3 treatment arms (placebo, 10-, 10-, 20-mg/kg TID, and 20-, 20-, 40-mg/kg TID), and mean triglyceride levels increased minimally in ataluren-treated patients. Similar changes were not seen in the double-blind study for nmCF (Study 009). In that study, low cholesterol levels were observed prior to treatment in >40% of patients across both treatment arms. No ataluren-treated patients shifted from normal cholesterol at baseline to high cholesterol at Week 48. Shifts from normal triglycerides at baseline to high triglycerides at Week 48 were observed in both treatment arms, and were somewhat higher in placebo. Despite the lack of effect of ataluren on total cholesterol and triglycerides in nmCF, total cholesterol and triglycerides will continue to be monitored throughout this study.

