- **Serum Electrolytes:** Assessments of serum electrolytes (sodium, chloride, potassium, bicarbonate, magnesium, calcium, and phosphorus) provide information regarding renal function that may supplement more primary assessments. Derangements in serum concentrations may reflect altered tubular handling of these ions. With worsening renal function, hyperphosphatemia and hypocalcemia may develop and reductions in serum bicarbonate or elevations in potassium may suggest an impaired ability of proximal tubules or collecting ducts to maintain acid-base balance [National Kidney Foundation 2002]. Given the cardiovascular and neurological consequences of severe derangements of serum potassium, calcium, or magnesium, evaluation of these ions is important to avoid potential secondary complications. Because transient Grade 1 alterations in the concentrations of electrolytes are very unlikely to be associated with significant

secondary side effects, alterations to  $\geq$ Grade 2 are considered appropriate to prompt potential interruption/modification of ataluren dosing.

- **Renal Ultrasound:** In considering the markers to be used for decision-making within the study, renal ultrasound is proposed because it is the central imaging modality for assessing the anatomy of the kidneys and urinary tract in children. The test can detect changes in kidney size, assess parenchymal cystic or mass lesions, evaluate the renal vasculature, and assess the collecting system [Avni 2004]. Renal ultrasound is a routine component of diagnostic algorithms for follow-up of serum or urinary abnormalities suggesting renal dysfunction [Barratt 2004] and will be among the diagnostic testing performed for this protocol as part of the assessment for such findings. It is safe, painless and convenient, providing advantages over contrast-enhanced computed tomography (CT) scanning (which has contrast-mediated nephrotoxicity and radiation risks) and magnetic resonance imaging (MRI) (which requires contrast administration and potential sedation in young children). Obtaining a baseline ultrasound enhances the sensitivity of subsequent ultrasonography, offering context for any potential abnormalities emerging during study drug treatment.

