6. ANALYSIS CHANGES FROM PROTOCOL

Due to the premature termination of the study, the time of withdrawal from the study analysis has been removed compared to current protocol version 3.0. The paired t-test on FEV₁ and the summary of FEF₂₅₋₇₅ have also been removed. On the other hand, the drug exposure adjusted incidence rate of TEAEs has been added. Summary of occurrence of TEAE has been added as well.

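### The SAP narrows the once-per-subject worst-grade laboratory tables to the nine Table 2 parameters, where the protocol planned them for each relevant assay, and SAP Section 6 does not declare the change

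*SAP*

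**What the plan says.** Protocol 11.4.5.2 applies CTCAE grading, where a scale exists, to hematology, biochemistry, adrenal and urine data. It then makes three separate commitments.

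- For graded assays: "Summary tables will be presented for each relevant assay to show the number of subjects by severity grade with corresponding percentages". Each subject is counted once per assay, at the worst grade.
- For parameters without a CTCAE scale: "the frequency of subjects with values below, within, and above the normal ranges will be summarized".
- For organ-specific monitoring: "Separate listings and tables will be created for assessment of adrenal, hepatic, and renal parameters based on the conditions listed in" Section 6.3.1, which contains the protocol's Table 2.

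SAP 4.10.2 says: "Frequency tables will be presented for safety monitoring parameters to show the number and percentages of subjects by severity grade categories defined in" Table 2. Where no CTCAE grade exists, "abnormal results will be summarized by protocol-defined thresholds as noted in" Table 2. The rule of one count per subject at worst grade follows in the same paragraph. SAP Table 2 has four hepatic rows (total bilirubin, ALT, AST, GGT) and five renal rows (cystatin C, creatinine, BUN, urine protein:creatinine, urine blood).

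SAP Section 6 records the departures from the protocol. It begins with "the time of withdrawal from the study analysis has been removed compared to current protocol version 3.0" and goes on to the FEV₁ paired t-test, the FEF₂₅₋₇₅ summary and two adverse-event additions. It names no laboratory output. SAP Section 1 gives the SAP precedence where the two documents conflict.

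**The concern.** Laboratory abnormalities are part of the primary endpoint, and their frequency and severity are among the things it is meant to describe. The most direct summary of that is the number of subjects who ever reached each grade on treatment. The protocol promised this for each relevant assay. Under the SAP it will be produced only for the hepatic and renal parameters in Table 2.

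The electrolytes show why this matters. The rationale in Protocol 14.2.3.1.2 says that changes to Grade 2 or above "are considered appropriate to prompt potential interruption/modification of ataluren dosing". They are not in Table 2, so the study report need not contain a count of subjects who ever reached Grade 2 for any of them. A reader who compares the report with the protocol will find planned tables missing and no explanation.

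**Working it through.** No power or error-rate calculation applies. The check compares the two texts, counts the tests, and asks what the remaining outputs can show.

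**1. Scope.**

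| | Protocol 11.4.5.2 | SAP 4.10.2 |
|---|---|---|
| Worst-grade table, one count per subject | Each relevant assay | Table 2 parameters |
| No CTCAE scale | Below / within / above normal | Table 2 thresholds; low/normal/high only in by-visit shift tables |
| Organ-specific tables | Additional to the above | The only worst-grade tables left |

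The protocol's relevant assays cannot sensibly mean the Table 2 parameters alone. The organ-specific tables based on Section 6.3.1 are announced as separate, after the per-assay tables.

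**2. Count.** The inputs are the test lists and Table 2 in SAP 4.10.2. Bilirubin fractions are counted separately; the white-cell differential and red-cell morphology are not split.

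- Listed: 29 biochemistry + 8 hematology + 11 urinalysis = 48.
- Table 2 rows: 4 + 5 = 9. They draw on 7 serum tests, urine blood, and urine protein and creatinine (one ratio): 7 + 1 + 2 = 10 tests.
- Outside Table 2: 48 − 10 = 38, made up of 22 biochemistry, 8 hematology and 8 urinalysis. 38/48 = 79%.

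This counts tests outside Table 2. It does not count lost worst-grade tables. The once-per-subject rule is a worst-grade rule, so it covers only graded assays, and the documents do not show which of the 38 have a CTCAE scale. The three adrenal assays (cortisol, renin, aldosterone) are not among the 48, because SAP 4.10.2 does not list them.

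**3. What remains for a gradable assay outside Table 2.**

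- *By-visit summaries and shift tables.* Each shift table runs from baseline to one visit. Suppose one Grade 2 value appears at Week 32 and one at Week 80. The tables look the same whether this is one subject or two. In general, if c_v subjects are at a grade at visit v, the number ever at that grade lies between the largest c_v and the sum of the c_v. The schedule has 192/16 = 12 on-treatment clinic visits after Week 1, so that range can be wide.
- *Visit definition.* SAP 5.2 uses the scheduled visits without window mapping, so unscheduled results have no stated place in these tables. The derived Final Visit is the last on-treatment value, not the worst.
- *Maximal and minimal change.* These are extremes over the study, but of numerical change, not of grade.
- *Listings.* They hold the data but give no count.
- *Adverse-event tables.* Under Protocol 9.1.1 a laboratory abnormality becomes an adverse event only if it needs intervention or further investigation and does not belong to an event already reported. Abnormalities that need no action are left to laboratory monitoring, so only laboratory outputs can show them.

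None of these gives the number of subjects who ever reached each grade.

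**4. Declaration.** Section 6 has three removals (time of withdrawal, FEV₁ paired t-test, FEF₂₅₋₇₅ summary) and two additions (exposure-adjusted TEAE rate, TEAE occurrences). None concerns laboratory tables.

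**The case against.** The best defence is that little is lost. The trial is open-label, with a single ataluren regimen, about 70 planned subjects, descriptive analyses only and an early stop. No comparison or decision rule depends on the missing counts. The SAP takes precedence, so nobody is in doubt about what will be run. An electrolyte abnormality that led to action would normally be reported as an adverse event and tabulated by worst grade with each subject counted once. All of this stands, and it is why the point is minor. It does not supply the missing count for abnormalities that needed no action, and a precedence clause does not declare a change.

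Four stronger readings are tempting, and the documents do not support them.

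- *That 79% of assays lose a promised worst-grade table.* For tests without a CTCAE scale, the protocol states no worst-value or ever-abnormal rule, only a low/normal/high frequency. The margins of the SAP's shift tables give that frequency by visit.
- *That the seven electrolytes are a firm minimum.* They come from rationale text, which treats them as supplementary to more primary assessments. Protocol 14.1.4 lists six and omits chloride, and nothing in the documents shows a CTCAE grade for chloride. They are an example, not a lower bound.
- *That the lipids were promised such a table.* Protocol 14.1.4 says that "total cholesterol and triglycerides will continue to be monitored throughout this study", and the by-visit outputs meet that.
- *That the protocol requires unscheduled results to be counted.* It refers only to a period of interest, which it leaves undefined.

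**Conclusion.** The narrowing is real and undeclared. For gradable assays outside the nine Table 2 parameters, the SAP drops the count of subjects at worst grade that the protocol planned, and no remaining table replaces it. Its extent is not determinable: 38 of 48 listed tests lie outside Table 2, and an unknown part of them is both relevant and gradable. The documents give no event rates for these assays, so the number of subjects concerned cannot be estimated either.

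The conclusion assumes that SAP 4.10.2 means what it says in tying the frequency tables to Table 2, and that Table 2 is complete as printed. Its abbreviation line defines electrolyte symbols, but neither document's table has an electrolyte row.

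A reader might infer that the primary endpoint goes unanalysed for these assays or that a safety signal would be hidden. That goes too far, because the data remain visible in by-visit tables, change summaries and listings. This is a minor point and a cheap improvement.

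**What to change.** Before database lock, amend SAP 4.10.2, as SAP Section 1 allows:

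- Restore the once-per-subject worst-grade frequency table for all CTCAE-gradable assays.
- Restore the below/within/above-normal frequency for assays without a scale.
- State the period over which the worst grade is taken.

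Including unscheduled post-baseline results is advisable, since the worst value may fall between visits that are 16 weeks apart, but this adds to the protocol's wording.

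If the restriction to Table 2 is deliberate, add one sentence to SAP Section 6 that says so and gives the reason.

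The cost is one extra table on data already collected, or that one sentence. No protocol change is needed.
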